## Study Protocol:

### 1. Objectives:

**Primary GOAL:** Compare efficacy and safety of prophylactic indomethacin, DCC, and their combination, in affecting the incidence and severity of IVH in infants less than 29wks GA at birth.

- **Aim 1A):** Test for differences in primary outcome measure: 'fraction of survivors with no severe IVH or PVL' among the 4 groups, using head ultrasound (1-30d), and head MRI at 38wks adjusted GA.
- **Aim 1B):** Test the hypothesis that DCC improves effectiveness and/or decreases toxicities of indomethacin.
- **Aim 1C):** Test for treatment dependent differences in neurocognitive follow up evaluations and investigate relationships between short term brain imaging results and later neurocognitive performance across treatment groups.

**Secondary GOAL:** Investigate mechanistic effects of prophylactic indomethacin, DCC, and their combination in infants less than 29wks GA.

- **Aim 2A):** Test the hypotheses that blood volume status and/or hemodynamic stability are different between groups (at 0,1,2,3,7, 30, and 60 days of life).
- **Aim 2B):** Test the hypothesis that biomarkers of inflammation and vascular endothelial stress are different between groups (at 0,1,2,3,7, 30, and 60 days of life).
- **Aim 2C):** Test the hypothesis that numbers, or apoptotic frequency, of circulating progenitor cells with endothelial or neuronal phenotype capacity are different between groups (at 0,1,2,3,7, 30 and 60 days of life).
- **Aim 3):** Determine relationships between clinical outcomes (Aim1) and blood measurements (Aim 2) among treatment groups.

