**6. Research Procedures:**

Following enrollment and consent at time of delivery the infant will be placed in one of four groups (per the following algorithm)

For the immediate cord clamping groups the obstetrician will clamp the umbilical cord immediately (<10sec) after birth, per standard procedure. For the delayed cord clamping groups the obstetrician will clamp the cord at 45 sec after delivery and hold the infant in a sterile bag (thermoregulatory bag) 10-15in below the mother's introitus at vaginal delivery or at/below the level of incision if a cesarean section is performed. A stopwatch will identify the time when the infants' buttocks are delivered from the vagina or the

uterus (or head if breech); time elapsed will be counted in 10sec intervals for the OB by the investigator. Infants in the DCC group will be placed into a sterile bag to minimize heat loss at the sterile field by the delivery OB. Per standard NICU clinical protocol, infants in the ICC groups will be placed in the thermoregulatory bag once they are placed on the neonatal warming bed.

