Infants will be brought to NICU once the infant is determined stable by the neonatal resuscitation team. The enrolled infant will then be cared for in the NICU using standard practices and started on either Indocin 0.1 mg/kg/day for 3 days (Groups C and D) or placebo (Groups A and B), depending on group assignment. Randomization of indomethacin is “blinded” to medical care team (physicians, nurses, clinic personnel). Maternal and infant clinical data and infant blood samples will be collected at specified times for measurement of mechanism-based endpoints. In addition to routine assessment of renal function via standard clinical measures of BUN and creatinine, renal function status will also be monitored by serum Cystatin C levels (0.1mL) at 7 and 30 DOL (these will be considered research measures, since they are not routinely measured in NICU patients). Measurements will be done with ELISA (50uL serum required) at [name]’s research lab. The oxygen saturation (SpO2) of all infants is continuously monitored upon admission to the NICU by a Masimo pulse-oximeter. Monitoring starts right after birth until discharge from the hospital. The SpO2 and heart rate waveforms stored in the Masimo pulse-oximeter will be downloaded for analysis. Some NICU beds have a different pulse oximeter (Nelcore) which does not allow for data downloads. If a patient is admitted to bedspace not equipped with a Masimo pulse oximeter, one will be placed but screen and alarms turned off. This is a minimal risk procedure and of no additional cost to the patient for data consistency purposes. A neonatal sleep study/pneumogram (respiratory inductance plethysmography, high-resolution pulse-oximetry and electrocardiography) will be performed on all subjects who are not intubated or on non-invasive ventilation at 30 and 60 days of life. In case infants remain intubated or on non-invasive respiratory support at 60 (55 – 65) DOL, a pneumogram will be performed as soon as that level of respiratory support is weaned or discontinued. The pneumogram is non-invasive and is of minimal risk to patients. All data collected will be measured/recorded by persons who are essentially ‘blinded’ to the delivery/treatment at birth.

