In summary, a total of 3.7 ml of blood (7 time points during the 0-60 days of life, 0.5mL each, and 2 time points with 0.1ml each), 4 head ultrasound measurements (day of life (DOL) three, first week of life, DOL fourteen and at 30 DOL or later), a head MRI at 38 weeks corrected GA will be obtained from each subject as well as 3 measurements of neurodevelopment (TIMP and Bayley III). Enrolled patients will receive a study number to protect confidentiality of demographic information. Data to be collected is shown on the attached data collection instrument. Only the Co-PIs and study coordinators will know the identities

of the patients and be responsible for the storage of collected data. All data will be de-identified.

Studies shown below are marked as part of standard care or research. The 14 day ultrasound is variable, depending on findings on the 7 day ultrasound. Our standard unit policy is to repeat at 14 days if our routine 7 day ultrasound shows a significant hemorrhage.

Timeline	Procedure	Standard Care	Research
at delivery	umbilical cord blood collection (1-5mL)		X
At admission, 24, 48, & 72hr, Days 7, 30, & 60	blood draw (0.5mL) at each time point	X	
72 hours	head ultrasound		X
7 & 30 days	head ultrasound	X	
7 & 30 days	Serum Cystatin C (0.1mL)		X
14 days	head ultrasound	X	X
Days 30 & 60 if not on vent, or as soon as possible when extubated	neonatal sleep study/pneumogram		X
38 weeks of corrected GA*	head MRI*		X
3-4 months of corrected GA	Test of Infant Motor Performance (TIMP)	X	
6-9 months of corrected GA	Bayley III	X	
18-24 months of corrected GA	Bayley III; Brief infant Toddler Social Emotional Assessment (BITSEA), MCHAT(pass/fail)	X	

\* , Please note that at the initial start of this 5 year study our plan for head MRIs in all enrolled patients is considered a research effort. Note however that the use of head MRI in extremely premature infants that are known to or suspected to have brain lesions is currently common-place and at other institutions is standard care. Therefore it is possible (and perhaps likely) that the routine use of this imaging modality will in coming years become 'standard care' for all preterm infants that are at very high risk of cranial bleeds (e.g. the exact patient group in this study) at our institution. If this becomes the case we will provide amendments to the IRB to account for this issue.

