- **Aim 2A)** Test the hypotheses that blood volume status and/or hemodynamic stability are different between groups (at 0,1,3,7,and 30 days of life).

- **Aim 2B)** Test the hypothesis that biomarkers of inflammation and vascular endothelial stress are different between groups (at 0,1,3,7,and 30 days of life).
- **Aim 2C)** Test the hypothesis that numbers, or apoptotic frequency, of circulating progenitor cells with endothelial or neuronal phenotype capacity are different between groups (at 0,1,3,7,and 30 days of life).

**Aim 2 Statistical analyses: Comparisons of biochemical and hemodynamic variables across treatments:** For Aim 2 we compare the blood sample variables (Hct, HB, Ferritin, CRP, IL6, TNF, s-ICAM, progenitor cell numbers, and apoptotic cell percentages) and summary measures of cardiovascular variables (blood pressure, pressor support and others) using a multivariate linear regression model (for continuous responses) and a multivariate logistic regression model (for nominal variables such as the need for inotropic/vasopressor support) regression analyses where influential demographic variables associated with mothers and infants will be used as covariates. The differences in the pattern of changes over time of the repeatedly measured cardiovascular status variables such as the blood pressure levels will be examined using repeated measures Analysis of Variance techniques and mixed effect ANOVA models. Influential covariates will be used for building a suitable predictive model using variable selection methods to identify the optimal variable set. Using this model, the hypotheses regarding the differences between the 4 groups and their interaction effect with time will be examined.

**Aim 3: Determine relationships between clinical outcome measures (Aim1) and blood measurements (Aim 2) among treatment groups.**

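### Aim 2 should treat the admission sample as an outcome for cord clamping but as a baseline for indomethacin; the plan does not separate the two

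*Combined protocol and SAP*

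**What the plan says.** **Times compared.** Section 1 (Objectives) tests whether the Aim 2 variables "are different between groups (at 0,1,2,3,7, 30, and 60 days of life". The SAP's restatement of Aims 2A to 2C tests whether they "are different between groups (at 0,1,3,7,and 30 days of life". Day 0 is in both lists.

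**Samples.** The timeline table in section 6 (Research Procedures) gives the blood draws as "At admission, 24, 48, & 72hr, Days 7, 30, & 60". That is seven draws, matching the seven days in section 1, so day 0 is taken here to be the admission draw. The table also has a separate delivery sample, "umbilical cord blood collection (1-5mL", with no stated role in the Aim 2 model.

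**Interventions.** In the immediate groups the obstetrician will "clamp the umbilical cord immediately (<10sec) after birth"; in the delayed groups clamping is at 45 seconds. Once in the NICU, infants are "started on either Indocin 0.1 mg/kg/day for 3 days (Groups C and D) or placebo (Groups A and B"). The hour of the first dose, and whether it comes before or after the admission draw, is not given.

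**Model.** For the Aim 2 regressions, "influential demographic variables associated with mothers and infants will be used as covariates". Repeated-measures ANOVA and mixed models are named for the cardiovascular variables, with covariates chosen by variable selection. The hypotheses are group differences and group by time: "the hypotheses regarding the differences between the 4 groups and their interaction effect with time will be examined". How sampling time enters the model for the blood biomarkers is not stated.

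**The concern.** The two randomized factors start at different moments. Clamping is over within a minute of birth, so the admission sample already carries any DCC effect. Study drug starts later, in the NICU, so for indomethacin the same sample is most plausibly a pre-treatment value. It therefore has two roles, and the plan assigns it only one: an outcome time for all four groups.

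For indomethacin this has two consequences:
- A difference averaged over times includes one time at which no drug effect is expected. It is pulled toward zero, and a chance imbalance at admission enters the average.
- A comparison at a single later time is not diluted, but it ignores the infant's own starting haematocrit, ferritin, IL6, s-ICAM, progenitor count or blood pressure.

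The obvious shortcut, adjusting every contrast for the admission value, would be wrong for DCC because it conditions on a post-intervention measurement and removes part of the DCC effect.

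At stake is the secondary goal, the mechanism of each treatment and of their combination.

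**Working it through.** **What can be reproduced.** The plan gives no power or effect size for Aim 2. Two sums agree with the text: 4 × 100 = 400 infants, and 7 × 0.5 mL + 2 × 0.1 mL = 3.7 mL. The second supports reading the admission draw as one of the seven.

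**Inputs from the documents.** K = 5 times (SAP) or K = 7 (section 1); m = K − 1 times after day 0; 100 infants per group, so 200 against 200 for indomethacin with the cord arms pooled.

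**Assumptions, not in the documents.** Unit variance at each time; no indomethacin effect at day 0 and a constant effect d afterwards; two-sided 0.05; correlation ρ of 0.3, 0.5 or 0.7, under compound symmetry or under AR(1) in visit order.

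**Formulas**
- Mean of all K times: effect d × m/K, variance vA. Under compound symmetry vA = (1 + (K − 1)ρ)/K.
- Mean of the m later times: effect d, variance vB = (1 + (m − 1)ρ)/m.
- The same mean adjusted for admission: effect d, variance vC = vB − c², where c is the covariance of the later mean with the admission value (c = ρ under compound symmetry).
- Gain in effective sample size = [vA/(m/K)²]/vC. Dropping day 0 without adjusting gives [vA/(m/K)²]/vB.
- Under AR(1), vA and vB are averages of ρ^|i−j| over the times used, and c = (ρ + … + ρ^m)/m.

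**Dilution of the averaged effect.** 4/5 = 0.80 with five times; 6/7 = 0.86 with seven.

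**Gain, seven times**

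| Structure | ρ | vA | vB | vC | Drop day 0 only | Drop and adjust |
|---|---|---|---|---|---|---|
| Compound symmetry | 0.3 | 0.400 | 0.417 | 0.327 | 1.31 | 1.67 |
| Compound symmetry | 0.5 | 0.571 | 0.583 | 0.333 | 1.33 | 2.33 |
| Compound symmetry | 0.7 | 0.743 | 0.750 | 0.260 | 1.35 | 3.89 |
| AR(1) | 0.3 | 0.240 | 0.276 | 0.270 | 1.19 | 1.21 |
| AR(1) | 0.5 | 0.348 | 0.391 | 0.364 | 1.21 | 1.30 |
| AR(1) | 0.7 | 0.518 | 0.563 | 0.445 | 1.25 | 1.58 |

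For example, under compound symmetry at ρ = 0.5: 0.571 × (7/6)² = 0.778, and 0.778/0.333 = 2.33. With five times, the compound-symmetry gains are 1.79, 2.50 and 4.17.

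**Power example.** d = 0.2, 200 against 200, seven times, ρ = 0.5, with z = effect/√(2v/200):
- Compound symmetry: all-times mean, z = 0.171/0.0756 = 2.27, power 0.62. Adjusted, z = 0.2/0.0577 = 3.46, power 0.93.
- AR(1): all-times mean, z = 0.171/0.0590 = 2.91, power 0.83. Adjusted, z = 0.2/0.0603 = 3.32, power 0.91.

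**Group-by-time test, same example, compound symmetry.** Noncentrality = 100 × d² × (m/K)/(1 − ρ) = 100 × 0.04 × (6/7)/0.5 = 6.86 on 6 df, power 0.46. With five times: 100 × 0.04 × 0.8/0.5 = 6.4 on 4 df, power 0.50, against 0.90 for the adjusted contrast.

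**A single later time.** Adjustment multiplies the variance by 1 − ρ², where ρ is that time's correlation with admission. The gain is 1/0.91 = 1.10, 1/0.75 = 1.33 or 1/0.51 = 1.96.

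**The case against.** A reader might infer that the indomethacin analysis is biased toward zero as written and that the baseline goes unused. The documents do not support that, for four reasons.

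1. The plan nowhere specifies an equal-weight average over times. The Aim 2 wording reads equally well as a comparison at each listed time, and those at later times are not diluted.
2. The plan also tests group by time. There the null difference at day 0 is part of the contrast, so dilution does not arise and the admission value is used implicitly. A truly multivariate model with day 0 as one response also uses it, through the correlation.
3. The mixed-model text names cardiovascular variables. For the biomarkers the handling of time is unstated, so one cannot say that their model pools all times alike. Nor is a baseline excluded: the mixed-model covariates are not limited to demographics.
4. That the admission draw precedes the first dose is an inference.

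The size also depends on the correlation structure. Compound symmetry makes admission predict day 60 as well as 24 h. Under AR(1) most of the gain comes from dropping day 0; adjustment adds a factor of only 1.02, 1.07 or 1.26. A constant effect to day 60 after a three-day course is also a favourable assumption.

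All of this stands and limits the claim. It does not remove it. The interaction test has about half the power of the adjusted contrast in the compound-symmetry example. It also means different things for the two factors: a DCC effect present at admission and constant afterwards gives no DCC-by-time interaction, while an equally sustained indomethacin effect does. The unstated order of draw and dose is itself a reason to act, since without it the meaning of day 0 for indomethacin is unknown.

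**Conclusion.** The point holds as a matter of precision and clarity in a secondary, mechanistic aim. Day 0 is a comparison time for all four groups, it comes after clamping, it probably comes before any drug effect, and no baseline is specified for indomethacin. Dilution to 0.80 (five times) or 0.86 (seven) applies only to differences averaged over times, and only if day 0 precedes the drug effect.

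With seven times, replacing the all-times mean by a later mean adjusted for admission is worth 1.7, 2.3 or 3.9 times the effective sample size under compound symmetry and 1.2, 1.3 or 1.6 under AR(1). The gain exceeds 1 in every case examined, but its size rests on an assumed constant effect and assumed correlations; an effect that fades by day 30 would change the figures. The primary endpoint is not affected.

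**What to change.** Replace the single four-group statement in the SAP's Aim 2 section with the following, for the biomarkers as well as the cardiovascular variables:

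- **Indomethacin against placebo, and the DCC-by-indomethacin interaction.** Analyse responses from 24 h onward with cord arm in the model. Either adjust for the same infant's pre-dose admission value, or fit one mixed model to all times that constrains the indomethacin difference at admission to zero within each cord arm. The mixed model also keeps infants without a pre-dose value. In the adjusted model, do not read the cord-arm coefficient as the DCC effect.
- **DCC against immediate clamping.** Keep the admission sample as an outcome and do not adjust for it.
- **Timing.** Record the times of the admission draw and the first study-drug dose, and use as baseline only values recorded as pre-dose.
- **Specification.** State how sampling time enters the biomarker models, and reconcile the five times in the SAP with the seven in section 1.

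The cost is SAP wording, two time stamps and a slightly more complex model. No new samples are needed.

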**Aim 3 Statistical analyses:** We will use our complete data set to investigate predictors of brain injury (IVH, or PVL), predictors of poor neurocognitive outcomes and the influence of treatment group on these predictive variables. Ultimately we will use the data collected in this project to identify which of our measured variables are the most 'useful' from a clinical perspective in forecasting outcomes in these high-risk patients. Significant variables for prediction will be identified using bivariate methods. Correlations will be utilized for two continuous variables. ANOVA, independent samples t-tests and independent samples nonparametric methods will be employed as appropriate for a nominal explanatory variable and a continuous variable. Pearson's chi-square and Fisher's exact statistic will be used as appropriate when both variables are nominal. For each outcome variable, appropriate multivariate modeling will be constructed using the identified significant variables from the bivariate analysis along with the grouping variables to ascertain the best reduced models for prediction. An alpha level of 0.05 is used for inclusion into the models. Any non-normally distributed continuous data will be corrected through appropriate transformations. Statistical software SAS 9.4 (SAS Institute, Cary, NC) and IBM SPSS Statistics (IBM Corp., Armonk, N.Y., USA) will be used for analyses. We have powered our study using chi-square tests for equality of proportions, but adopted analysis strategy that controls for influential covariates will generally improve the power. ***In all settings we will also perform separate analyses of IVH alone, and PVL alone.***

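### Aim 3 does not require a blood predictor of IVH or PVL to precede the lesion, so samples drawn at or after its detection can enter the forecasting models

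*Combined protocol and SAP*

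**What the plan says.** The SAP's Aim 3 heading is: "Determine relationships between clinical outcome measures (Aim1) and blood measurements (Aim 2) among treatment groups". The analysis text beneath it begins "We will use our complete data set to investigate predictors of brain injury (IVH, or PVL), predictors of poor neurocognitive outcomes" and gives the eventual purpose as to "identify which of our measured variables are the most 'useful' from a clinical perspective in forecasting outcomes in these high-risk patients". Candidates are screened one at a time by bivariate tests. Those that pass go into multivariable models with the treatment groups, at an inclusion level of 0.05, and these are cut down to the best reduced models.

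The markers come from Aim 2, where the SAP names nine "blood sample variables (Hct, HB, Ferritin, CRP, IL6, TNF, s-ICAM, progenitor cell numbers, and apoptotic cell percentages". Sampling times are given three times:

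- Protocol section 1 (Aim 2B): "biomarkers of inflammation and vascular endothelial stress are different between groups (at 0,1,2,3,7, 30, and 60 days of life".
- Section 6, timeline table: "At admission, 24, 48, & 72hr, Days 7, 30, & 60". The table also lists cord blood at delivery.
- SAP, Aim 2A to 2C: days 0, 1, 3, 7 and 30 only.

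Brain imaging in section 6 is "4 head ultrasound measurements (day of life (DOL) three, first week of life, DOL fourteen and at 30 DOL or later", plus a head MRI at 38 weeks corrected age. The day 14 scan is described as variable, since unit policy repeats the scan then if day 7 shows a significant bleed. For the Aim 1 ultrasound endpoint the SAP uses days 0-30.

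No section sets a landmark time, a lag, time-updated predictors, or an exclusion of infants whose lesion is already visible. The survival methods under Aim 1 compare treatment groups for the primary endpoint; they are not applied to the Aim 3 predictors.

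**The concern.** A forecast can use only what is known when it is made. If a day 7 or day 30 value is compared between infants with and without a lesion already visible at 72 hours, the test cannot separate a marker that precedes injury from one changed by the injury or its care. Haematocrit, haemoglobin, CRP and the cytokines could plausibly change in that way. Later samples also exist only for infants still alive.

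What is at stake is Aim 3's own question. A model containing post-lesion values could discriminate well and still be useless at the bedside, because those values do not exist when a forecast is needed. Better variable selection or validation would not cure this: a consequence of injury is reproducibly associated with injury.

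**Working it through.** **The schedule.** The documents give no lesion rate, effect size or power to reproduce. The one stated figure tied to the sampling schedule is the blood volume in section 6: 7 × 0.5 mL + 2 × 0.1 mL = 3.7 mL. This agrees with the text and supports seven draws, so the SAP's five-time list is the one out of line.

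**Draws against imaging** (nine named blood variables, assumed measured at every time; cord blood not counted):

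| | Protocol timeline | SAP list |
|---|---|---|
| Draw times | 7 | 5 |
| Variable-by-time candidates | 9 × 7 = 63 | 9 × 5 = 45 |
| Before the 72 h scan | 3 times, 27 candidates | 2 times, 18 candidates |
| At or after the 72 h scan | 4 times, 36 (57%) | 3 times, 27 (60%) |
| Strictly after the 72 h scan | 3 times, 27 (43%) | 2 times, 18 (40%) |
| At or after the end of the day 0-30 window | 2 times, 18 | 1 time, 9 |

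**Draws against the MRI.** Entry is below 29 weeks 6 days (section 3), so the oldest eligible infant is born at 29 weeks 5 days, or 208 days. Taking the MRI at exactly 38 weeks, or 266 days, it falls at least 266 − 208 = 58 days after birth. Day 30 blood therefore precedes the MRI in every eligible infant. Day 60 blood precedes it when gestational age is below 266 − 60 = 206 days, that is, below 29 weeks 3 days.

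**Illustration of the screen.** Documented inputs: N = 400 (section 4) and an inclusion level of 0.05 (Aim 3), taken as two-sided and applied to the bivariate test. Assumed inputs: lesion rate 10%, 15% or 20%; a marker with no difference before the lesion that shifts by d SD because of it; all 400 infants sampled after the lesion. With n1 infants with and n0 without the lesion, the pass probability is approximately Φ(d√(n1·n0/N) − 1.96).

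- 10%: √(40 × 360/400) = 6. For d = 0.3, Φ(1.8 − 1.96) = 0.44; for d = 0.5, Φ(3.0 − 1.96) = 0.85.
- 15%: √(60 × 340/400) = 7.14. For d = 0.3, 0.57; for d = 0.5, 0.95.
- 20%: √(80 × 320/400) = 8. For d = 0.3, Φ(2.4 − 1.96) = 0.67; for d = 0.5, Φ(4.0 − 1.96) = 0.98.

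The apparent AUC is Φ(d/√2): 0.58 for d = 0.3 and 0.64 for d = 0.5. A simulation of 4,000 trials per setting gave 0.44 and 0.84 at 10%, and 0.66 and 0.98 at 20%. The pre-lesion sample of the same marker passed 4-5% of the time.

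**The case against.** The strongest reply is that the SAP nowhere says day 7-60 blood will be set against an earlier bleed. The sentence on the data set covers neurocognitive outcomes too, for which every draw comes in time, and the Aim 3 heading speaks of relationships, so association is within scope. This stands as a limit. A reader might infer that consequences of injury will be reported as forecasters; the documents show only that they can be, with nothing to stop it. The gap remains because the same paragraph makes forecasting the purpose.

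A reader might also infer that day 30 and day 60 blood can never be a valid predictor of brain injury. The MRI arithmetic rules that out: for a lesion first seen on MRI, day 30 blood always precedes detection and day 60 blood does so for infants born before 29 weeks 3 days.

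Third, one might infer that treatment-group comparisons of the markers are spoiled. As Aim 2 comparisons they remain randomised contrasts; a lesion on the pathway changes their interpretation, not their validity.

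Other points narrow the claim without removing it. The lesion rates and shifts are assumptions. Not every infant will have a late sample. Passing the screen is not the same as surviving into the reduced model. A scan dates detection, not onset, so even a 24 h or 48 h sample may follow a bleed. Aim 3 is secondary, and the primary endpoint and safety analyses are untouched.

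**Conclusion.** The concern holds for the Aim 3 models of IVH and PVL. They lack a time-order rule, and 4 of 7 protocol draws or 3 of 5 SAP draws fall at or after the first scheduled scan. Those counts use document figures only. The inference that such values are eligible rests on the unrestricted data set and the absence of any limiting text, not on an explicit statement. The pass rates of 44-98% are illustrative and depend on the assumed shifts of 0.3-0.5 SD, lesion rates of 10-20% and complete sampling of 400 infants. Neurocognitive prediction is unaffected. The change should be made, but it does not bear on the trial's primary conclusion.

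**What to change.** Add to Aim 3 of the SAP that a blood or haemodynamic variable counts as a predictor of IVH or PVL only if it was measured before the first imaging, ultrasound or 38-week MRI, that shows the lesion. Fit the models as landmark analyses in infants alive and lesion-free on imaging at the landmark:

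- **Lesions first seen at the 72 h scan or later:** cord, admission, 24 h and, if retained, 48 h values.
- **Lesions first seen after a clear day 7 scan:** values up to day 7.
- **Lesions first seen on later imaging such as the MRI:** day 30 or day 60 values may be added where they precede that imaging.

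Label values measured at or after detection as associations. State that imaging dates detection and not onset, so the rule is a minimum and some early draws may still follow a bleed. Leave all draws available for the TIMP and Bayley models. Reconcile the five sampling times in the SAP with the seven in the protocol, which also settles whether the 48 h value exists for this analysis.

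The change needs no new data or visits. Its cost is fewer candidate predictors, fewer lesions in the later landmark analyses, and coarse dating of late lesions: because the day 14 scan is variable, an infant clear at day 7 may not be scanned again until day 30.

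### Aim 3 selects predictors by bivariate tests at 0.05 and fits its prediction models on the same infants without correcting for the selection, so some variables named as useful are likely to be chance findings

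*Combined protocol and SAP*

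**What the plan says.** The paragraph headed Aim 3 Statistical analyses, in the Statistical analysis plan, sets out the following sequence.

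- **Purpose:** to find which measured variables are "most 'useful' from a clinical perspective in forecasting outcomes in these high-risk patients".
- **Data:** the whole data set. No part is held back.
- **Screen:** "Significant variables for prediction will be identified using bivariate methods" (correlations, t-tests, ANOVA, nonparametric tests, chi-square or Fisher's exact test, according to variable type).
- **Threshold:** "An alpha level of 0.05 is used for inclusion into the models".
- **Model:** for each outcome, the screened variables and the treatment-group variables go into a multivariable model "to ascertain the best reduced models for prediction".

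The candidates are not listed for Aim 3. Aim 2 Statistical analyses names nine blood variables ("Hct, HB, Ferritin, CRP, IL6, TNF, s-ICAM, progenitor cell numbers, and apoptotic cell percentages"), together with cardiovascular summaries and demographic covariates. The Aim 2 statements in the analysis plan give five sampling times ("at 0,1,3,7,and 30 days of life"); section 1, Objectives, gives seven ("at 0,1,2,3,7, 30, and 60 days of life").

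Neither the protocol nor the analysis plan mentions a hold-out sample, cross-validation, bootstrap, shrinkage, multiplicity control, a limit on predictors per event, or a measure of discrimination or calibration. The one reference to validation, under Aim 1, concerns the assumptions of the Cox model.

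**The concern.** A variable that passes a 0.05 test in a sample has been chosen partly because its association in that sample is large. If the model is then fitted and judged on the same infants, its coefficients and apparent accuracy are biased upward. Unrelated variables also enter at about 1 in 20 of those tested. The usual protections are to validate the model, shrink it, or estimate the optimism, and the plan has none of these.

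What is at stake is a clinical statement about which measurements forecast brain injury or poor neurocognitive outcome in very preterm infants. A marker named by chance could be carried into later studies or bedside use. A model that looks moderately accurate could have no accuracy in new infants.

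**Working it through.** The plan gives no figure for Aim 3 (no candidate count, event count or performance target), so there is none to reproduce.

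**Inputs from the documents**
- 400 infants, 100 per group (section 4).
- Threshold 0.05 per test; no multiplicity adjustment is stated.
- Nine named blood variables (Aim 2 Statistical analyses).
- Five sampling times in the analysis plan, seven in the Objectives.
- At least three outcomes: IVH, PVL and neurocognitive outcome.

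**Assumptions, because the documents are silent**
- 10–20% of infants have the outcome.
- Values of one marker at different times correlate 0.5.
- No candidate truly predicts. This isolates what the procedure produces from noise alone.
- Candidate count *m*: 9 if each marker is reduced to one summary; 9 × 5 = 45 or 9 × 7 = 63 if every time point is screened. Cardiovascular and demographic variables would add to these.

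**False entries per outcome**

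Expected number = 0.05 × *m*, whatever the correlation. If tests are independent, the chance of at least one = 1 − 0.95^*m*. The correlated column is from simulation.

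| Candidates | Expected false entries | At least one, independent | At least one, correlation 0.5 |
|---|---|---|---|
| 9 | 0.05 × 9 = 0.45 | 1 − 0.95^9 = 37% | 35–37% |
| 45 | 0.05 × 45 = 2.25 | 1 − 0.95^45 = 90% | 82–85% |
| 63 | 0.05 × 63 = 3.15 | 1 − 0.95^63 = 96% | 90–92% |

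With nine candidates there is one value per marker, so the two probability columns differ only by simulation error.

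Over three outcomes the expected totals are 3 × 0.45 = 1.35, 3 × 2.25 = 6.75 and 3 × 3.15 = 9.45.

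**Apparent accuracy**

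Each simulated trial had 400 infants, a t-test screen at p<0.05 and a logistic model on the variables selected. AUC was computed on the building data and on fresh data.
- Selected markers only, 9 to 63 candidates: mean apparent AUC 0.53–0.66; in new infants 0.50.
- With the three group indicators also in the model, as the plan intends, 45 or 63 candidates and correlation 0.5: mean apparent AUC 0.62–0.68; in new infants 0.50.

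**Effect of the reduction step**

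The plan speaks of reduced models but names no rule. With backward elimination at 0.05, 15% events, correlation 0.9 between haematocrit and haemoglobin, 0.3 between other markers and 0.5 within a marker:
- 63 candidates: 1.3 noise variables remain on average, 87% chance of at least one, apparent AUC 0.60.
- 45 candidates: 1.0 remain, 76%, AUC 0.59.
- 9 candidates: 0.3 remain, AUC 0.53.

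Reduction makes the problem smaller but does not remove it.

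**The case against.** - **Candidate count.** The plan does not say that every marker-by-time value is screened, so 63 is the top of a range that starts at 9. Also, the Aim 1A analysis uses head ultrasound to day 30. A day-60 sample cannot forecast that finding, and a day-30 sample hardly can. Restricting the analysis plan's times to days 0, 1 and 3 leaves 9 × 3 = 27 candidates, 0.05 × 27 = 1.35 expected false entries and a 1 − 0.95^27 = 75% chance of at least one. This stands: the size must be given as a range.
- **Accuracy.** A reader might infer that Aim 3 will publish an inflated AUC. The plan names no accuracy measure, so the documents support only a conditional statement: any accuracy computed on the building data would be optimistic. The problem of chance predictors does not depend on this.
- **Noise only.** A reader might infer that the models will be wholly noise. That would require that none of the measured variables predicts outcome, and nothing in the documents says so. If real predictors exist, the models would mix real and chance entries.
- **Which step 0.05 governs.** The sentence could refer to the screen or to entry into the multivariable model. The problem is the same under either reading.
- **Materiality.** Aim 3 looks for relationships and comes last. This stands as a limit on importance. The plan does not call Aim 3 exploratory, however, and its stated purpose is clinical forecasting.

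**Conclusion.** The point holds as a cheap improvement. Following the stated rule makes chance predictors likely when time points are screened separately (82–92% per outcome with 45 or 63 candidates). They remain a material possibility with one summary per marker (35–37%). Pure-noise models would show an apparent AUC of 0.53–0.66, against 0.50 in new infants.

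These figures rest on the assumed 10–20% event rate, the within-marker correlation of 0.5 and the absence of true predictors. Correlation between markers and a reduction step lower them.

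It should not be inferred that the trial's main result is compromised. The procedure belongs to Aim 3, and the randomised comparison of the four groups is unaffected.

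**What to change.** Amend the Aim 3 paragraph of the analysis plan as follows.

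1. Fix the candidate list in advance for each outcome, stating whether each marker enters as one summary or as separate time points. Admit only measurements taken before that outcome is determined.
2. Force in gestational age, alongside the treatment-group variables that the plan already includes.
3. Report AUC and calibration corrected for optimism by a bootstrap that repeats the whole procedure (screen, reduction and fit) in every resample.
4. Report how often each variable is selected across resamples, so that unstable predictors are visible.

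Penalised regression (LASSO or elastic net) in place of the 0.05 screen is a reasonable option but not essential, because the bootstrap can be wrapped around the existing screen.

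The cost is a little more programming, with no new data, visits or infants. The downside is that reported accuracy will look less favourable.
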